The presence or absence of abnormalities consistent with lower respiratory tract infection on chest X-ray and/or CT scan as assessed by the local radiologist should be documented at screening (obtained no more than 10 days prior to dosing) and at Day 29 ( $\pm 3$  days). If no routine clinical radiological imaging of the chest is available at either of these timepoints, a chest X-ray should be obtained (chest CT scan is not a study-mandated procedure; however, the results of chest CT scan[s] performed as part of a participant's standard clinical care may be used for the purposes of the study). For those participants who cross over, chest imaging as described above should be documented within 7 days prior to Day 1' of the Cross-Over Period and at Day 29' ( $\pm 3$  days) of the Cross-Over Period. If the Day 29 imaging from the Primary Study Period falls within the 7-day window prior to cross over, this imaging need not be repeated prior to the participant entering the Cross-Over Period (ie, the Day 29 imaging will serve as the baseline imaging for the Cross-Over Period). All chest X-rays and/or CT scans will also be submitted for central reading, which will be used for analysis purposes.

For evaluation of potential renal, urinary tract, and pancreatic manifestations of AdV infection, a urinalysis (dipstick and microscopy) will be obtained at the local laboratory at Day 1 and Day

---

---

29, and serum amylase and lipase levels will be included in the clinical chemistry evaluations at the central laboratory.

Blood samples will be obtained from all participants for the measurement of posoleucel cell persistence through Week 24.

Repeat or unscheduled samples may be taken based on symptoms, for safety reasons, or for technical issues with the samples.

Safety assessments will include adverse event (AE) monitoring, clinical laboratory assessments, physical examinations, vital sign measurements, and 12-lead electrocardiograms (ECGs).

Additional safety assessments may be performed throughout the duration of the study if clinically indicated.

AEs of special interest (AESIs) include the following:

- Acute or chronic GVHD
- CRS
- Infusion-related reactions (IRRs)
- Graft failure and rejection

---

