Abbreviations: AdV = adenovirus; ALT = alanine aminotransferase; AST = aspartate aminotransferase; BAL = bronchoalveolar lavage; CBC = complete blood count; CIBMTR = Center for International Blood and Marrow Transplant Research; CMV = cytomegalovirus; COA = clinical outcome assessment; COVID-19 = coronavirus disease 2019; CSF = cerebrospinal fluid; CT = computed tomography; DNA = deoxyribonucleic acid; ECG = electrocardiogram; EQ-5D = European Quality of Life 5 dimension; ET = Early Termination; FSH = follicle-stimulating hormone; GVHD = graft versus host disease; HCT = hematopoietic cell transplant; HLA = human leukocyte antigen; ICU = intensive care unit; I/E = inclusion and exclusion; IV = intravenous(ly); LFT = liver function test; MAGIC = Mount Sinai Acute GVHD International Consortium; NA = not applicable; PBMC = peripheral blood mononuclear cell; qPCR = quantitative polymerase chain reaction; SpO2 = peripheral capillary oxygen saturation; VST = virus-specific T cell.

**Table 2. Schedule of Activities for Cross-Over Period (Participants with AdV Target Organ Disease by Week 10 of the Primary Study Period)**

Study Week (Cross-Over Period)	■	■	■	■	■	■	■	■	■	■	■	■	
Study Day (Cross-Over Period)	■	■	■	■	■	■	■	■	■	■	■	■	
Visit Window (Days)	NA	NA	±2	±2	±3	±3	±3	±5	±5	±28	±28	±42	NA
Study Procedures													
Cross-over I/E criteria [3]	X												
Prior and concomitant medications	X	X	X	X	X	X	X	X	X	X	X	X	
Pregnancy test [4]	X	X			X				X	X	X	X	
Study treatment administration [5]			X		X								
Infusion site evaluation [6]		X			X								
Post-infusion monitoring [7]		X			X								
COA (EQ-5D) [8]		X				X			X		X	X	
Adverse events	X	X	X	X	X	X	X	X	X	X	X	X	
Hospital information [9]	X	X	X	X	X	X	X	X	X	X	X	X	
Physical examination [10, 11]	X	X	X	X	X		X				X	X	
Weight [12]	X	X										X	X
Vital signs including SpO 2 [11, 13]	X	X	X	X	X	X	X	X	X	X		X	X
12-lead ECG [14]	X	X			X								
Chest X-ray and/or CT scan [15]	X						X						
Urinalysis [16]	X	X					X					X	X
Hematology and clinical chemistry [16]	X	X	X	X			X		X	X	X	X	
Coagulation (PT, INR, and PTT) [16]		X					X						
Adenovirus viral load in blood and stool with viral DNA extraction and storage [16, 17]	X	X	X	X	X	X	X	X	X	X	X	X	

Study Week (Cross-Over Period)	■	■	■	■	■	■	■	■	■	■	■	■	■
Study Day (Cross-Over Period)	■	■	■	■	■	■	■	■	■	■	■	■	■
Visit Window (Days)	NA	NA	±2	±2	±3	±3	±3	±5	±5	±28	±28	±42	NA
Study Procedures										X			

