7. Participants will be monitored closely and must remain in the clinic for ≥1 hour after the end of each infusion. Vital signs will be measured at the end of the infusion, and at 15, 30, 45, and 60 minutes after the end of the infusion. Participants must also remain on continuous pulse oximetry for ≥30 minutes after the end of the infusion. Post-infusion monitoring should be completed for all infusions of study treatment.

8. EQ-5D may be performed up to 24 hours prior to study treatment administration.
9. Includes information on hospital admission and discharge, ICU transfer, oxygen supplementation, and ventilation.
10. A complete physical examination will be performed at cross-over unless one has been completed within the past 3 days. Abbreviated physical examinations will be performed at all subsequent visits.
11. On days when study treatment is administered, perform vital signs and physical examination before study treatment administration.
12. Weight at cross-over should be used for all doses.
13. Vital signs include body temperature, heart rate, respiratory rate, SpO2, and systolic and diastolic blood pressure. Vital signs will be collected after the participant has rested for at least 5 minutes in the supine position.
14. Performed within 1 hour after study treatment administration on [REDACTED]
15. All participants will have imaging performed and analyzed locally as long as the imaging can be transmitted to the central reader. Images (chest X-ray and/or CT scan) obtained as part of a participant's standard clinical care may be used for the purposes of the study. If standard clinical imaging is not performed at these time-points, a chest X-ray should be performed for the purposes of the study. For those participants who cross over, chest imaging should be documented within 7 days prior to Day 1' of the Cross-Over Period, and at Day 29' ( $\pm 3$  days) of the Cross-Over Period.
16. Sample must be obtained prior to infusion of study treatment.

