For participants whose AdV viral load as determined by the Central Laboratory has decreased  $\geq 0.5 \log_{10}$  copies/mL AdV DNA between Day 1 and Day 8 or 11, the second dose will be from the same VST line/placebo lot as the first dose. When possible, the Day 11 value should be used to make this determination; however, if a Day 11 value is not available, the Day 8 value can be used. For participants whose AdV viral load has decreased  $<0.5 \log_{10}$  copies/mL AdV DNA between Day 1 and Day 8 or 11, the second dose will be with a new VST line from a different donor or placebo from a different lot. When possible, the Day 11 value should be used to make this determination; however, if a Day 11 value is not available, the Day 8 value can be used. In that case, the VST line chosen for the participant's second infusion will be the VST line with the next-best match according to the CytoMatch hierarchy as described above and will come from a different donor than the first VST line infused, while maintaining a threshold of at least 2 HLA allele matches between the VST line and the virus-infected recipient. The choice of second dose for participants who enter the Cross-Over Period will use the same criteria (with AdV viral load assessment on Day 11' [or Day '8, if Day 11' value is not available] to support the second dose on Day 15').

In the unlikely event that a suitable VST line for the second infusion cannot be identified in the bank, a second dose of the first VST line infused will be substituted for the participant's second infusion.

For participants who receive an additional dose for recurrence, the additional dose will be from the same VST line or placebo lot and include the same number of cells as the second dose. An additional dose for recurrence can only be administered after Day 29 of the Primary Study Period (the primary endpoint), but prior to 20 weeks. Participants who receive an additional dose for recurrence are not eligible for subsequent cross-over, and participants who have previously entered the Cross-Over Period are not eligible for a subsequent additional dose.

Once the lots of drug product have been selected, the treating physician will review and approve documentation that accompanies the drug product shipment prior to dose administration.

Randomization of patients to posoleucel versus placebo will occur only after VST line matching and selection has been confirmed (to satisfy inclusion criteria).

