### 10.3.1 Efficacy Analyses

All efficacy endpoints will be analyzed and formally compared between randomized treatment groups using statistical tests based on data from the Primary Study Period. In addition, for purposes of complete reporting, results for these endpoints will be reported, if appropriate, for data from the Cross-Over Period by treatment received in the Cross-Over Period, but no formal comparisons or statistical tests will be made.

The primary and key secondary efficacy endpoints will be analyzed under the estimand framework. The estimand attributes will be described in detail in the SAP.

In order to control the overall type 1 error rate, a sequential approach will be used to analyze the primary and key secondary efficacy endpoints, with undetectable viremia (less than LLOQ) at Day 29 of the Primary Study Period as the primary efficacy endpoint, followed by progression from viremia to target organ disease (for participants without target organ disease at screening), progression of target organ disease (for participants with target organ disease at screening), or non-relapse mortality during the study as the key secondary efficacy endpoint.

For AdV viral endpoints at Day 29 or Week 4 visit, a 14-day window will be applied to the Day 29 visit. The last observed plasma AdV DNA result through Day 29 + 14 days (up to 43 days post first infusion) will be used for the analysis. Participants who cross over on or before Day 29 will be treated as failure.

All efficacy endpoints will be analyzed based on the mITT Population, and these analyses will be considered the primary analyses of efficacy. The primary and key secondary efficacy endpoints will also be analyzed based on the ITT and PP Population to assess the robustness of the primary analysis results.

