2.2 Study Design

2.2.1 *Overview*

This is a Phase 3, multicenter, randomized, double-blind, placebo-controlled study to assess the safety and efficacy of posoleucel as compared to placebo for the treatment of AdV infection in pediatric and adult recipients of HCT with AdV infections receiving SoC.

Approximately 80 participants may be randomized [] to receive [] infusions of posoleucel or placebo []). Randomization will be stratified []

It is expected that no more than 30% of participants, but at least 10% of participants, will be []. Enrollment of participants <1 year of age will occur once preliminary safety data are available from 5 participants ≥ 1 and ≤ 6 years of age. The Data Safety Monitoring Board (DSMB) will review data through Day 29 from these 5 participants once available and make a recommendation. A formal memo will be provided to ethics committees and sites once the DSMB approves enrollment of participants <1 year of age.

The Primary Study Period is 4 weeks (28 days) for evaluation of efficacy, including the primary endpoint, plus 20 weeks for safety follow-up, for a total study duration of 24 weeks. For participants who cross over, the Cross-Over Period is 4 weeks (28 days), plus 20 weeks for safety

[figure not shown]
follow-up. Participants who experience recurrence and receive an additional dose will have safety follow-up for 20 weeks after the final dose.

Participants who progress to active target organ disease or whose existing target organ disease progresses (as assessed by the Investigator and Sponsor Medical Monitor and based on the criteria in Appendix 8 of the protocol) between Day 29 and Week 10 will be considered to have experienced progression and will have the option to be crossed over to the alternate treatment arm. Participants can cross over before Day 29 only if they progress with target organ disease as adjudicated by the Adjudication Committee. Cross-over participants will receive the alternate treatment to which they were originally randomized, posoleucel or placebo [redacted] sequential infusions separated by [redacted] \pm 3 days), but study treatment will remain blinded.

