3.4 Efficacy Analyses

Only the primary efficacy endpoint will be summarized for the primary treatment period based on the mITT Population.

For AdV viral endpoints at Day 29 or Week 4 visit, a +14-day window will be applied to the Day 29 visit. The last observed plasma AdV DNA result through Day 29 + 14 days (up to 43 days post first infusion) will be used for the analysis for all the participants including those who crossover from PSL to placebo. For participants who crossover from placebo to PSL, the pre-dose cross-over Day 1 viral load may be used. Participants who cross over on or before Day 29 will be treated as failure.

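### For cross-overs infused on Days 30–43, SAP 3.4 reads the primary endpoint by a different rule in each randomized arm and makes the placebo-arm rule optional

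*SAP*

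**What the plan says.** SAP 3.4 takes the last plasma AdV DNA result through Day 29 plus 14 days. It says this result "will be used for the analysis for all the participants including those who crossover from PSL to placebo". The next sentence covers the opposite direction: "For participants who crossover from placebo to PSL, the pre-dose cross-over Day 1 viral load may be used". Anyone who crosses over on or before Day 29 is a failure in both arms.

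Cross-over remains open after Day 29. Under SAP 2.2, participants whose organ disease progresses "between Day 29 and Week 10 will be considered to have experienced progression and will have the option to be crossed over". A first cross-over infusion on Days 30–43 is therefore possible.

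Protocol 10.3.1 states the window once, without a split by arm: "The last observed plasma AdV DNA result through Day 29 + 14 days (up to 43 days post first infusion) will be used". The same section bases formal efficacy comparisons on Primary Study Period data and reports Cross-Over Period results separately, by treatment received in that period. Protocol 5.1 sets a new baseline at the first cross-over infusion and counts up to 10 weeks in the Primary Study Period followed by 24 weeks in the Cross-Over Period. SAP 3.1, 3.4 and 3.4.2 also place the endpoint in the primary period.

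**The concern.** The mITT analysis is by randomized treatment (SAP 3.2.2), so cross-over direction identifies the randomized arm. A rule that depends on direction is therefore a rule that depends on arm.

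This has three consequences:

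- **Unequal reading time.** A posoleucel-arm participant can be credited with clearance up to Day 43. A placebo-arm participant with the same history may be cut at the pre-dose sample.
- **Discretion.** Neither document says when 'may' applies or who decides. The placebo count, the difference, its confidence interval and the logistic estimate can change with the analyst's choice.
- **No end date on the placebo sentence.** Cross-over runs to Week 10. Read literally, the sentence could admit a pre-dose value taken well after Day 43.

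The primary endpoint is the only efficacy result this SAP will report, and the SAP was written after the trial had been stopped for futility. Its derivation should leave no choices open.

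**Working it through.** **1. The plan's own figure.** Protocol 10.1 gives 82 participants, or 41 per arm (Protocol 5.2), for 0.55 vs 0.25, two-sided alpha 0.05, 80% power and a chi-square test. With mean rate 0.40: n = [1.960·√(2·0.40·0.60) + 0.842·√(0.55·0.45 + 0.25·0.75)]² / 0.30² = (1.358 + 0.555)² / 0.09 = 40.7, so 41. The figure reproduces. It is used below only as a denominator.

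**2. The two rules side by side.** Take a first cross-over infusion on Day 32. Day 8' falls on Day 39 and Day 11' on Day 42.

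| Randomized arm | Value read under SAP 3.4 |
|---|---|
| Posoleucel (crosses to placebo) | Last result by Day 43, here Day 42, after the cross-over infusion |
| Placebo (crosses to posoleucel) | Pre-dose Day 32 if the option is used; Day 42 if it is not |

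**3. Which period the later results belong to.** Because the Cross-Over Period has its own baseline at the first cross-over infusion, the Primary Study Period ends there. The Day 39 and Day 42 results are then Cross-Over Period data, and counting them conflicts with the restriction to primary-period data in Protocol 10.3.1 and the SAP.

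**4. Which infusion days matter.** On dosing days the rule is "Sample must be obtained prior to infusion of study treatment" (Table 2, note 16), so Day 1' is pre-dose in both arms. The first scheduled viral load after infusion on Day D is Day 8' = D + 7. Table 2 redacts the visit days, so the ±2-day window for Day 8' is inferred from column order.

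- D + 7 ≤ 43 gives D ≤ 36.
- D + 5 ≤ 43 gives D ≤ 38.

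Later infusions matter only through unscheduled samples, which the protocol allows: "Repeat or unscheduled samples may be taken based on symptoms, for safety reasons, or for technical issues with the samples".

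**5. Effect of one participant.** 1/41 = 2.4 points; 1/20 = 5.0 points. The 20 is an assumption: about 40 at the interim, allocated 1:1.

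**6. Illustration, all inputs assumed.**

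- Fraction of an arm infused on Days 30–43: f = 0.05 to 0.10.
- Infusions spread evenly, so the share with a scheduled post-infusion value by Day 43 is 7/14 = 0.50 to 9/14 = 0.64.
- Cleared at pre-dose: c = 0.10. Rebound: r = 0.10. Late clearance: g = 0.20 without posoleucel effect, 0.35 after posoleucel.
- Net gain from later reading: q = (1 − c)g − c·r. This is 0.9·0.20 − 0.01 = 0.17, or 0.9·0.35 − 0.01 = 0.305 after posoleucel.

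*Option used, no treatment effect:* tilt toward posoleucel = f × share × 0.17.

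- f = 0.05: 0.43 to 0.55 points.
- f = 0.10: 0.85 to 1.09 points.

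The sign reverses if g < c·r/(1 − c) = 0.01/0.90 = 0.011.

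*Option not used, posoleucel works:* the placebo percentage rises by f × share × 0.305, which is 0.76–0.98 points (f = 0.05) or 1.52–1.96 points (f = 0.10). The posoleucel arm is also read late, at q = 0.17. Compared with pre-dose reading in both arms, the difference moves by f × share × (0.17 − 0.305), about 0.3–0.4 points (f = 0.05) or 0.7–0.9 points (f = 0.10) toward placebo.

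**7. Scale.** The Newcombe 95% interval for equal rates near 25% has a half-width of 18.3 points at 10/41 vs 10/41 and 25.9 points at 5/20 vs 5/20.

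**The case against.** **Each half has a reason.** Contamination by active drug occurs only from placebo to posoleucel, so cutting those participants at pre-dose keeps posoleucel's effect out of the placebo percentage. Keeping results after a placebo infusion resembles SAP 3.4.2, which retains data after treatment discontinuation. This stands as an explanation. It supports a mandatory cut in the placebo arm, however, not an optional one, and it does not justify longer reading time in the other arm alone.

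**'May' can be read narrowly.** Day 1' is labelled a cross-over visit, so the sentence may simply admit that pre-dose sample as the last primary-period value. That is plausible and would agree with the primary-period restriction. The SAP does not say so, and on this reading the posoleucel-arm rule is the one out of line.

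**The size is assumed.** This also stands. Protocol Appendix 10 reports a delay of about 5 days from randomization to infusion. If cross-over product took as long and progression were assessed from Day 29, infusions would start near Day 34. The affected share would be 3/10 to 5/10, and the first tilt would be 0.05·0.3·0.17 to 0.10·0.5·0.17, about 0.3 to 0.9 points.

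**Stronger readings the documents do not support.** A reader might infer:

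- *That the SAP favours posoleucel.* The direction depends on how 'may' is read and on whether posoleucel works.
- *That late clearance is common in this group.* The Amendment 3 rationale describes participants with declining viremia, not those whose organ disease progressed.
- *That the tilt could reach 7 points.* Taking 6 cross-overs per arm with a 50% chance of clearing gives 6·0.5/41 = 7.3 points. The documents support neither input, and the Day 8' timing limit is ignored.
- *That a pre-dose cut departs from the protocol.* The window sentence taken alone has no cut at cross-over, but the same section limits comparisons to primary-period data.

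**Conclusion.** The defect is real and minor. SAP 3.4 derives the endpoint by different rules in the two arms for first cross-over infusions after Day 29 and by Day 43, and leaves the placebo-arm rule to choice. The result is a possibly tilted and not fully reproducible descriptive estimate.

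The documents do not give the number affected, and it may be zero. Under the assumed inputs the tilt is about 1 point or less in either direction, against interval half-widths of 18 to 26 points. The text of the rule is certain. The size rests wholly on assumed cross-over, clearance and rebound rates.

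A reader might go further and doubt the futility decision or compute a loss of power. The documents support neither: SAP 3.1 rules out hypothesis tests, and the futility analysis belongs to a separate plan that is not among them. Cross-overs on or before Day 29 are unaffected.

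**What to change.** In SAP 3.4, end the window sentence where it says the result is used for the analysis. Replace the arm-specific text with one mandatory rule:

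> For any participant whose first cross-over infusion falls after Day 29 and by Day 43, in either direction, the last plasma AdV DNA result on or before Day 43 and before that infusion (including pre-dose Day 1') will be used; results after Day 43 are not used under this window.

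Then:

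- Report the number of these cross-overs by arm.
- Add one sensitivity row using the last result through Day 43 regardless of cross-over. Label it as including Cross-Over Period data, not as the protocol's rule.
- Describe the main rule as applying the Day 43 window within the Primary Study Period. Do not call it a departure from the protocol. If the database is already locked, record it in the CSR as a deviation from the SAP, as SAP 1 provides.

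The cost is a wording change, one count and one table row, with no new data. The downside is that a few post-cross-over results in the posoleucel arm drop out of the main summary; they remain visible in the sensitivity row.

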3.4.1 Primary Efficacy Endpoint Analysis

3.4.2 Primary Analysis of Primary Efficacy Endpoint

The primary efficacy endpoint, undetectable viremia (less than LLOQ) at Day 29 of the Primary Study Period, will be summarized by treatment group using the count and percentage, together with an exact (Clopper-Pearson) 95% confidence interval for the true percentage. The difference in percentages between the two treatments (posoleucel – placebo), together with a 95% exact confidence interval for the true difference, will be presented.

This endpoint will be analyzed using logistic regression. The model will include a term for treatment and the following covariates: level of viremia at Baseline ($\geq 10,000$ copies/mL or $< 10,000$ copies/mL AdV DNA), age (≥ 12 years or < 12 years) and absolute lymphocyte count at Baseline. For participants who discontinued treatment but remain on the study, data collected after treatment discontinuation will be included in the analysis. If a participant doesn't have plasma AdV DNA result in the Day 29 through Day 43 window but has undetectable viremia before Day 29 and after Day 43, it will be imputed as success for the primary endpoint. The deaths related to adenovirus infection on or before Day 29 will be imputed as failure.

Subgroup analyses of the primary endpoint will be performed for both of the randomization stratification variables: (1) level of viremia: $\geq 10,000$ copies/mL and $< 10,000$ copies/mL AdV DNA and (2) age: ≥ 12 years or < 12 years.

